7. STATISTICAL METHODS AND DETERMINATION OF SAMPLE SIZE

7.1 STATISTICAL DESIGN – MODEL

The primary objectives of this trial is to investigate the safety and tolerability of BI 894416 by using descriptive statistics for all endpoints comparing active dose groups to placebo. The primary endpoint is defined in Section [2.1.2](#). Inferential statistics is not planned (as explained in section 7.2)

Secondary objectives are the exploration of PK of BI 894416 endpoints as specified in section [2.1.3](#) by descriptive statistics.

7.2 NULL AND ALTERNATIVE HYPOTHESES

Safety and tolerability of the different dose groups of BI 894416 are to be determined on the basis of the investigated parameters in comparison to placebo. It is not planned to test any statistical hypotheses. Instead, they will be described in their entirety and evaluated by descriptive statistical methods.

Any confidence intervals computed are to be interpreted in the perspective of the exploratory character of the trial; i.e., confidence intervals are considered as interval estimates for effects.

7.3 PLANNED ANALYSES

Analysis sets

Statistical analyses will be based on the following analysis sets:

- Treated set (TS): The treated set includes all subjects who were randomized and treated with at least one dose of investigational medicinal product. The treatment assignment will be determined based on the first treatment the subjects received. The treated set will be used for safety analyses.
- Pharmacokinetic parameter analysis set (PKS): This set includes all subjects in the treated set (TS) who provide at least one PK endpoint that was not excluded due to a protocol violation relevant to the evaluation of PK or due to PK non-evaluability (as specified in the following subsection ‘Pharmacokinetics’). Thus, a subject will be included in the PKS, even if he contributes only one PK parameter value for one period to the statistical assessment. Descriptive and model based analyses of PK parameters will be based on the PKS.

Adherence to the protocol will be assessed by the trial team. Important protocol deviation (IPD) categories will be specified in the TSAP, IPDs will be identified no later than in the Report Planning Meeting, and the IPD categories will be updated as needed.

Pharmacokinetics

The pharmacokinetic parameters listed in Section [2.1](#) will be calculated according to BI internal standard operating procedure (SOP). Noncompartmental pharmacokinetic parameters will be calculated based on actual sampling times using a validated pharmacokinetic software (e.g., Phoenix® WinNonlin®).

Plasma and urine concentration data and parameters of a subject will be included in the statistical PK analyses if they are not flagged for exclusion due to a protocol violation relevant to the evaluation of PK (to be decided no later than in the Report Planning Meeting) or due to PK non-evaluability (as revealed during data analysis, based on the criteria specified below). Exclusion of a subject's data will be documented in the CTR.

Relevant protocol violations may be

- Incorrect trial medication taken, i.e. the subject received at least one dose of trial medication the subject was not assigned to
- Incorrect dose of trial medication taken
- Use of restricted medications

Plasma and urine concentrations and/or parameters of a subject will be considered as non-evaluable, if for example

- The subject experienced emesis that occurred at or before two times median t_{max} of the respective treatment (Median t_{max} is to be determined excluding the subjects experiencing emesis),
- Missing samples/concentration data at important phases of PK disposition curve.

Plasma/urine concentration data and parameters of a subject which is flagged for exclusion will be reported with its individual values but will not be included in the statistical analyses.

Only concentration values within the validated concentration range and actual sampling times will be used for the calculation of pharmacokinetic parameters. Concentrations used in the pharmacokinetic calculations will be in the same format as in the bioanalytical report (that is to the same number of decimal places provided in the bioanalytical report).

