3.2 DISCUSSION OF TRIAL DESIGN, INCLUDING THE CHOICE OF CONTROL GROUP(S)

For single -rising dose trials, the sequential rising dose design described in Section [3.1](#) is viewed favourably under the provision not to expose the subjects to undue risks, since the main trial objective is to investigate safety and tolerability of BI 894416.

Single-blind conditions regarding the subject's treatment (active or placebo) are maintained within each dose group. However, subjects and investigators will be aware of the dose of the drug administered. The disadvantage of this trial design is a possible observer bias with regard to the dose-dependent effects; in addition, the sequential dosing of groups could potentially result in time-related effects. However, as such effects are expected to be small relative to the differences between the doses in the broad range investigated, unbiased comparisons between treatments can still be expected.

It is standard in single rising dose trials involving healthy subjects to include a placebo group to control for safety and tolerability of the trial medication. Each dose group consists of 8 subjects, with 6 on active treatment, and 2 on placebo. For data analysis purposes, the placebo control group will include all subjects that were treated with placebo, regardless of the groups they were treated. Six subjects per active treatment group are generally considered to be sufficient for the exploratory evaluation of pharmacokinetics.

For this trial, 25 mg has been selected as the minimum dose, which may be required to achieve therapeutic systemic exposure to BI 894416. However, higher doses might still be well tolerated while providing a larger magnitude of therapeutic effects. Finally, even if the therapeutic dose is determined to be as low as 25 mg, higher than therapeutic doses are typically explored in Phase I trials to provide a safety margin for following trials e.g., drug-drug-interaction trials, trials with patients with impaired excretion function, etc., where substantial increases in exposure may be seen.

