7.3.4 Safety analyses

Safety will be assessed as defined by the endpoints listed in Section [2.1.2](#) and [2.2.2](#) based on the treated set (TS). Safety analyses will be descriptive in nature and will be based on BI standards.

For all analyses the treatment actually administered (= treatment at onset) to the subject will be used (any deviations from the randomised treatment will be discussed in the minutes of the Report Planning Meeting).

Treatments will be compared in a descriptive way. The placebo group in the safety evaluation will consist of all subjects treated with placebo, regardless of the dose group in which they were treated. The test treatment groups will be compared to the placebo group in a descriptive

Proprietary confidential information © 2020 Boehringer Ingelheim International GmbH or one or more of its affiliated companies

way. Tabulations of frequencies/proportions will be used for the evaluation of categorical (qualitative) data, and tabulations of descriptive statistics will be used to analyse continuous (quantitative) data.

Measurements (such as ECGs, vital signs, or laboratory parameters) or AEs will be assigned to treatments (see Section [4.1](#)) based on the actual treatment at the planned time of the measurement or on the recorded time of AE onset (concept of treatment-emergent AEs).

Therefore, measurements planned or AEs recorded prior to intake of trial medication will be assigned to the screening period, those between the trial medication intake and the individual subject's end of REP (see Section [1.2.1](#)) will be assigned to the treatment period.

Events occurring after the REP but prior to trial termination date will be assigned to 'follow-up'. These assignments including the corresponding time intervals will be defined in detail in the TSAP. Note that AEs occurring after the last per protocol contact but entered before database lock will be reported to Pharmacovigilance only and will not be captured in the trial database.

Additionally, further treatment intervals (called analysing treatments) may be defined in the TSAP in order to provide summary statistics for other than above periods, such as combined treatments, on-treatment totals, or periods without treatment effects (such as screening and post-trial intervals).

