7.6 RANDOMISATION

The first 4 subjects per dose level will not be randomised to maintain a treatment sequence of active-placebo-active-active due to safety reasons. The remaining 4 subjects of each dose level will be randomised in a 3:1 ratio, which reflects the ratio of subjects receiving active drug to placebo.

The sponsor will arrange for the randomisation as well as packaging and labelling of trial medication. The randomisation list will be generated using a validated system that uses a pseudo-random number generator and a supplied seed number so that the resulting allocation is both reproducible and non-predictable.

The randomisation list will contain additional blocks to allow for subject replacement (refer to Section [3.3.5](#)).

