6. GENERAL ANALYSIS DEFINITIONS

6.1 TREATMENTS

For basic study information on investigational products, assignment of treatments and selection of doses, please see CTP, Section 4.

The study was performed as a single-blind, randomised, placebo-controlled study in healthy male Japanese subjects. It was planned that 24 subjects will be treated with a single dose of BI 894416 or Placebo. The study comprises 3 dose groups. Each dose group was planned to consist of 8 subjects randomised to active treatment or Placebo (6 on active treatment, 2 on Placebo).

Table 6.1: 1 Treatments and labels used in the analysis

Dose group	Treatment	Short label
P*	Placebo, tablet, qd	Placebo
A	25mg BI 894416 tablet, po, qd	BI 25mg
B	50mg BI 894416 tablet, po, qd	BI 50mg
C	70mg BI 894416 tablet, po, qd	BI 70mg

*The placebo control group will include all subjects that were treated with placebo, regardless of the groups they were treated.

The study was prematurely stopped after the first dose group (25mg BI 894416). Therefore, all analyses will be performed for this dose group only (Placebo n=2, BI 25mg n=6).

Section 1.2.2 of CTP:

The Residual Effect Period (REP (...)) of BI 894416 has not been defined yet. (...)

Conservatively, a minimum period of 14 days after last administration of BI 894416, or placebo, has been selected as the REP. Therefore, the individual subject's end of trial will be 14 days following last dosing with BI 894416, or placebo, at the earliest.

All adverse events (AE) reported between administration of trial medication and the individual subject's end of trial will be counted as on-treatment AEs.

The following study phases will be defined for the analysis:

- **Screening** (ranging from 0:00 h on day of informed consent until time of administration of trial medication (BI 894416 or Placebo))
- **On treatment** (ranging from the time of administration of trial medication until 336 hours (14 days) after time of administration)
- **Follow-up (F/U)** (ranging from 336 hours (14 days) after administration of trial medication until 0:00 h on day after trial termination date)

Section 7.3.4 of the CTP: *Note that AEs occurring after the last per protocol contact but entered before final database lock will be reported to Pharmacovigilance only and will not be captured in the trial database.*

The following AE displays will be provided in the report:

Section 15.3 and Appendix 16.1.13.1.8 (for ClinicalTrials.gov) of the CTR displays:

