6.3 SUBJECT SETS ANALYSED

Section 7.3 of the CTP:

- *Treated set (TS): The treated set includes all subjects who were randomized and treated with at least one dose of investigational medicinal product. The treatment assignment will be determined based on the first treatment the subjects received. The treated set will be used for safety analyses.*
- *Pharmacokinetic parameter analysis set (PKS): This set includes all subjects in the treated set (TS) who provide at least one PK endpoint that was not excluded due to a protocol violation relevant to the evaluation of PK or due to PK non-evaluability (as specified in the following subsection 'Pharmacokinetics'). Thus, a subject will be included in the PKS, even if he contributes only one PK parameter value for one period to the statistical assessment. Descriptive [...] analyses of PK parameters will be based on the PKS.*

(...)

Pharmacokinetics

Plasma and urine concentration data and parameters of a subject will be included in the statistical PK analyses if they are not flagged for exclusion due to a protocol violation relevant to the evaluation of PK (to be decided no later than in the Report Planning Meeting) or due to PK non-evaluability (as revealed during data analysis, based on the criteria specified below). Exclusion of a subject's data will be documented in the CTR.

Relevant protocol violations may be

- *Incorrect trial medication taken, i.e. the subject received at least one dose of trial medication the subject was not assigned to*
- *Incorrect dose of trial medication taken*
- *Use of restricted medications*

Plasma and urine concentrations and/or parameters of a subject will be considered as non-evaluable, if for example

- *The subject experienced emesis that occurred at or before two times median t_{max} of the respective treatment (Median t_{max} is to be determined excluding the subjects experiencing emesis),*
- *Missing samples/concentration data at important phases of PK disposition curve.*

[figure not shown]
Plasma/urine concentration data and parameters of a subject which is flagged for exclusion will be reported with its individual values but will not be included in the statistical analyses.

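### Does the treated set leave out the four subjects per dose level who are not randomised?

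*Protocol*

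**What the plan says.** Protocol 7.3 sets two conditions for the treated set: "The treated set includes all subjects who were randomized and treated with at least one dose of investigational medicinal product". SAP 6.3 quotes this rule unchanged, admitting "all subjects who were randomized and treated with at least one dose of investigational medicinal product". The primary endpoint (Protocol 7.3.1) and all safety analyses (SAP 7.8) use this set, and the pharmacokinetic set is drawn from it.

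Protocol 7.6 describes allocation within each dose level of eight: "The first 4 subjects per dose level will not be randomised to maintain a treatment sequence of active-placebo-active-active due to safety reasons". It continues: "The remaining 4 subjects of each dose level will be randomised in a 3:1 ratio".

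SAP 6.1 uses the word randomised more broadly: "Each dose group was planned to consist of 8 subjects randomised to active treatment or Placebo". After noting the stop at the first dose group, it gives the numbers to be analysed: "all analyses will be performed for this dose group only (Placebo n=2, BI 25mg n=6".

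On the control group, Protocol 3.2 says "For data analysis purposes, the placebo control group will include all subjects that were treated with placebo", and Protocol 7.3.4 says "The placebo group in the safety evaluation will consist of all subjects treated with placebo".

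**The concern.** An analysis-set definition should produce the set it names. Here one condition for entry is randomisation, and the section that describes randomisation says half of each dose group is not randomised. A programmer who applied both statements literally would drop the four fixed-sequence subjects from the treated set, and therefore from the pharmacokinetic set.

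SAP Section 7 takes percentages over all subjects in the relevant set, so the definition fixes the denominators. On the literal reading they would halve, from 6 to 3 on active and from 2 to 1 on placebo, and each subject with a drug-related adverse event would count for twice as many percentage points. In a group of eight that would matter.

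A second, smaller worry is that SAP 6.1 calls all eight subjects randomised. If the report repeated this, it would misdescribe how half of them were allocated.

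**Working it through.** **Inputs**

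- Dose group size: 8, with 6 active and 2 placebo (Protocol 3.1); three groups planned, 24 subjects in total.
- First four subjects per level: active, placebo, active, active, not randomised (Protocol 7.6).
- Remaining four per level: randomised 3:1 (Protocol 7.6).
- Numbers to be analysed after the stop: 6 on BI 25 mg and 2 on placebo (SAP 6.1).

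**Reproducing the plan's figure**

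- Fixed sequence: 3 active + 1 placebo.
- Randomised part: 4 × 3/4 = 3 active; 4 × 1/4 = 1 placebo.
- Sum per group: 3 + 3 = 6 active and 1 + 1 = 2 placebo, so 8.
- Over three groups: 3 × 8 = 24.

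Both totals match the documents.

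**Literal reading of the definition**

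- Only the randomised part qualifies: 3 active + 1 placebo = 4 of 8.
- The pharmacokinetic set could then hold at most 3 active subjects.

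The 6 and 2 in SAP 6.1 can therefore be reached only by counting the fixed-sequence subjects. The literal reading and the stated numbers cannot both hold.

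**Which reading the plan supports**

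1. SAP 6.1 states the analysed numbers outright. SAP Section 4 shows that the document was written after the trial had stopped, so these numbers describe a closed group.
2. Within the SAP the terms agree with each other: eight subjects are called randomised, the treated set takes those randomised and treated, and eight are analysed. The conflict appears only against Protocol 7.6.
3. Protocol 4.1.3 gives subjects numbers from the randomisation list in order of arrival and assigns treatment from that list, with no exception for the first four. The natural reading is that all eight hold list entries and that Protocol 7.6 describes how the first four entries are ordered, although neither document says so directly.
4. Protocol 3.2, Protocol 7.3.4 and the footnote to SAP Table 6.1: 1 all define the placebo group by treatment received. The literal rule would lose one of the two placebo subjects and so contradict all three.
5. SAP 6.2 looks for protocol deviations in all treated subjects, and SAP 7.8 reports safety data for treated subjects who do not complete. Nothing suggests that a treated subject would be left out.

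**Effect of rewording**

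Subjects analysed before and after: 8 and 8. Denominators before and after: 6 and 2 in both cases. The difference is zero.

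**The case for a change.** The best case for a change is that the error is plain and costs almost nothing to correct. A sequence printed in the protocol is not random, and being entered on a list does not make it so. Protocol 7.6 says expressly that these subjects are not randomised, and no sentence says that they count as randomised for the treated set. The SAP authors also had the opportunity: in the same quotation in SAP 6.3 they cut the reference to model-based analyses because of the early stop, yet kept the randomisation condition. Separately, the description in SAP 6.1 is wrong for half the group whoever is analysed.

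The inconsistency does stand, and SAP 6.1 does use the word loosely. But the proposed correction would leave every subject, denominator and table as they are. The label also carries little weight here. Protocol 7.2 plans no hypothesis tests. Investigators know the treatment of all eight subjects (Protocol 4.1.5.1), and the list is sent to the site in advance (Protocol 4.1.3), so the randomised half is not concealed from the site either. The worry about the report concerns a document not under review. Its authors have the fixed sequence in front of them in Protocol 7.6, and SAP Section 3 refers readers to the protocol for randomisation.

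**Conclusion.** This is a clerical inconsistency in one word, and no change to the plan is needed. Read alone, the definition gives 4 of 8 subjects; read with the rest of the plan, it gives 8 of 8, which is what SAP 6.1 says will be analysed. Analysts will resolve it correctly because the SAP gives them the group sizes, and a treated set of 3 and 1 would visibly fail to match.

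The effect on the primary endpoint, the other safety outputs and the pharmacokinetic summaries is nil. The conclusion rests on two assumptions: that the analysis follows the numbers stated in SAP 6.1, and that the report takes its description of allocation from Protocol 7.6. Nothing in either document suggests otherwise.

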7.3.1 Primary endpoint analyses

The primary endpoint as specified in Section [2.1.2](#) will be derived according to BI standards. The analysis will be based on the treated set (TS) and will be descriptive in nature.

7.3.2 Secondary endpoint analyses

Primary analyses

The secondary endpoints (refer to Section [2.1.3](#)) will be analysed descriptively. Analyses will be performed for the parent drug.

Further exploratory analyses

Proprietary confidential information © 2020 Boehringer Ingelheim International GmbH or one or more of its affiliated companies

Dose proportionality will be explored via graphical checks and if applicable via the power model stated below. The analysis will be performed for the pharmacokinetic endpoints $AUC_{0-\infty}/C_{max}$ specified in Section [2.1.3](#).

The power model describes the functional relationship between the dose level and PK endpoint on the log scale via

[figure not shown]
$$y_{km} = \log(x_{km}) = \mu + \beta \cdot \log(D_k) + e_{km},$$

where

y_{km} logarithm of response (PK parameter) measured on subject m receiving dose k,
 x_{km} response (PK parameter) measured on subject m receiving dose k,
 μ the overall mean,
 β slope parameter of linear regression line,
 D_k level of dose k, $k=1, \dots, 3$,
 e_{km} the random error associated with the m^{th} subject who was administered dose k
($e_{km} \sim N(0, \sigma^2)$ iid).

The slope parameter β together with its two-sided 90% confidence interval will be estimated. Additionally, the r-fold change $r^{\beta-1}$ together with its 90% CI will be derived.

As some small doses at the beginning and/or some doses at the upper end might not contribute to the linear relationship between dose and PK, dose proportionality over the entire dose range investigated might not be shown. In that case an attempt will be made to identify a subrange of at least 3 consecutive doses where dose proportionality can be concluded.

7.3.4 Safety analyses

Safety will be assessed as defined by the endpoints listed in Section [2.1.2](#) and [2.2.2](#) based on the treated set (TS). Safety analyses will be descriptive in nature and will be based on BI standards.

For all analyses the treatment actually administered (= treatment at onset) to the subject will be used (any deviations from the randomised treatment will be discussed in the minutes of the Report Planning Meeting).

Treatments will be compared in a descriptive way. The placebo group in the safety evaluation will consist of all subjects treated with placebo, regardless of the dose group in which they were treated. The test treatment groups will be compared to the placebo group in a descriptive

Proprietary confidential information © 2020 Boehringer Ingelheim International GmbH or one or more of its affiliated companies

way. Tabulations of frequencies/proportions will be used for the evaluation of categorical (qualitative) data, and tabulations of descriptive statistics will be used to analyse continuous (quantitative) data.

Measurements (such as ECGs, vital signs, or laboratory parameters) or AEs will be assigned to treatments (see Section [4.1](#)) based on the actual treatment at the planned time of the measurement or on the recorded time of AE onset (concept of treatment-emergent AEs).

Therefore, measurements planned or AEs recorded prior to intake of trial medication will be assigned to the screening period, those between the trial medication intake and the individual subject's end of REP (see Section [1.2.1](#)) will be assigned to the treatment period.

Events occurring after the REP but prior to trial termination date will be assigned to 'follow-up'. These assignments including the corresponding time intervals will be defined in detail in the TSAP. Note that AEs occurring after the last per protocol contact but entered before database lock will be reported to Pharmacovigilance only and will not be captured in the trial database.

Additionally, further treatment intervals (called analysing treatments) may be defined in the TSAP in order to provide summary statistics for other than above periods, such as combined treatments, on-treatment totals, or periods without treatment effects (such as screening and post-trial intervals).

Adverse events will be coded using the Medical Dictionary for Regulatory Activities (MedDRA). Frequency, severity, and causal relationship of AEs will be tabulated by treatment, system organ class and preferred term. SAEs, AESIs (see Section [5.2.6.1](#)) and other significant AEs (according to ICH E3) will be listed separately.

Previous and concomitant therapies will be presented per treatment group without consideration of time intervals and treatment periods.

Laboratory data will be compared to their reference ranges. Values outside the reference range as well as possibly clinically significant values will be highlighted in the listings. Additionally, differences from baseline will be evaluated.

Vital signs or other safety-relevant data will be assessed with regard to possible on-treatment changes from baseline.

The ECG variables QT, HR, QTcF, QTcB, PR, QRS, and RR obtained from the centralised evaluation of 12-lead ECG recordings will be the basis for the derivation of quantitative and categorical ECG endpoints. These endpoints and their analyses will be described in the TSAP.

